### 15.2 Protocol Review and Amendments

Information regarding study conduct and progress will be reported to the Institutional Review Board (IRB) per the current institutional standards of each participating center. Any changes to the protocol will be made in the form of an amendment and must be approved by the IRB of each institution prior to implementation.

The Protocol Chair (or designee) is responsible for the coordination and development of all protocol amendments, and will disseminate this information to the participating centers.

Before implementing this study, the protocol, the proposed informed consent form and other information to subjects, must be reviewed by a properly constituted Institutional Review

Board/Independent Ethics Committee (IRB/IEC/REB). Any amendments to the protocol, other than administrative ones, must be approved by this committee.

Amendments significantly affecting the safety of subjects, the scope of the investigation or the scientific quality of the study, require additional approval by the IRB/IEC/REB. Amendments affecting only administrative aspects of the study do not require formal protocol amendments or IRB/IEC/REB approval but the IRB/IEC/REB of each center must be kept informed of such administrative changes.

### 15.3 Informed Consent

The investigator (or his/her designee) will explain to each subject the nature of the study, its purpose, the procedures involved, the expected duration, the potential risks and benefits involved and any discomfort it may entail. Each subject will be informed that participation in the study is voluntary, that s/he may withdraw from the study at any time, and that withdrawal of consent will not affect her subsequent medical treatment or relationship with the treating physician(s) or institution. The informed consent will be given by means of a standard written statement, written in non-technical language, which will be IRB approved. The subject should read and consider the statement before signing and dating it, and will be given a copy of the document. No subject will enter the study or have study-specific procedures done before his/her informed consent has been obtained.

In accordance with the Health Information Portability and Accountability Act (HIPAA), the written informed consent document (or a separate document to be given in conjunction with the consent document) will include a subject authorization to release medical information to the Coordinating Center and supporting agencies and/or allow these bodies, a regulatory authority, or Institutional Review Board access to subjects' medical information that includes all hospital records relevant to the study, including subjects' medical history.

### 15.4 Confidentiality and Disclosure

The investigator agrees to keep all information provided by this study in strict confidence and to request similar confidentiality from his/her staff and the IRB/IEC/REB. Study documents provided (protocols, investigators' brochures, CRFs and other material) will be stored appropriately to ensure their confidentiality.

Patient medical information obtained by this study is confidential, and disclosure to third parties other than those noted below is prohibited. Upon the patient's permission, medical information may be given to his or her personal physician or other appropriate medical personnel responsible for his or her welfare. This medical information must be made available to the IRB and DSMC, upon request, for source verification of study documentation. Data generated by this study must be available for inspection upon request by representatives of the U.S. FDA, local health authorities, [name] and her authorized representative(s), collaborators and licensees, and the IRB for each study site, if appropriate. We will make all reasonable efforts to keep patient's protected health information (PHI) private and confidential. We will only utilize or relinquish this kind of information according to federal privacy guidelines. There are many safeguards in place to prevent the unintentional disclosure of information obtained for or produced by this study. Research data, including the data collected from the medical charts will be entered into a password-protected database. Any publications or public disclosure of data relating to the patient's tumor will be done without any identifying information.

PHI will be collected and stored in the ONCORE research database. The coordinating center will have access to all research data, which will be kept for at least 2 years after the study is

completed. Any research data entered in a patient medical record will be stored for an indefinite amount of time. There are no plans to destroy data at this time.

Confidentiality and security will be maintained for the tissue collection within this study. All tissue samples obtained for this study will be assigned a code and this code used to identify the sample. The samples will not be labeled with the patient's name, address or other information that would identify them. All information will be coded to maintain privacy. Research data, including the data collected from the medical charts will be entered into a password-protected database. The database (Breast Cancer Program Database) in which this study data are going to be stored has a firewall (in addition to the institutional firewall) with the highest level of protection, i.e. the same level of protection as the on-line hospital information system at Vanderbilt. This means that users must log on to a web server that sits between the institutional firewall and the firewall to the database, and only this application server is allowed to query the database. Information, including the identifier and password for the authorized users, is transmitted via a secure shell protocol using 128k encryption. Only [name], the PI, and the Breast Team Data Manager, approved through our IRB will be allowed access to patient identifiers. Other levels of authorization may exist for approved users, e.g. access to de-identified data. This database will store a de-identified link to the patient data and will not otherwise store patient data, even de-identified data. The safety monitoring will be performed by the groups deemed appropriate by the Vanderbilt University Medical Center IRB for reviewing the clinical trials procedure. Safety monitoring for the database is also performed by the Networking and Security Services of the Vanderbilt University Medical Center. Audit trails for access to the web server and the databases behind the dual firewall system are maintained in accordance with the practices of the Networking and Security Services of the Vanderbilt University Medical Center.

The investigator agrees to keep all information provided by Janssen Research & Development in strict confidence and to request similar confidentiality from his/her staff and the IRB/IEC/REB. Study documents provided by Janssen Research & Development (investigators' brochures and other material) will be stored appropriately to ensure their confidentiality. The information provided by Janssen Research & Development to the investigator may not be disclosed to others without direct written authorization from Janssen Research & Development, except to the extent necessary to obtain informed consent from patients who wish to participate in the trial.

### 15.5 Records Retention

The investigator will retain the records of the clinical trial (including, but not necessarily limited to, CRFs, source documents, informed consent forms, drug accountability records, IRB correspondence, etc.) for at least 2 years after all investigations have been discontinued. Study records must be stored in a safe and secure location permitting timely retrieval, if necessary.

Study records that must be retained include case report forms, signed informed consents, correspondence with the IRB, study drug dispensing and inventory records, source documents (clinic charts, medical records, laboratory results, radiographic reports) and screening/ enrollment logs.

### 15.6 Study Termination

The investigator reserves the right to terminate the study at any site and at any time. Reasons for study termination may include, but are not limited to, the following:

- Investigator non-compliance with the protocol, GCP or regulatory requirements
- Insufficient enrollment
- Safety concerns

- Decision by Janssen Research & Development to modify or discontinue the development or manufacturing of erdafitinib
- A request to discontinue the study by the IRB or FDA

The investigator will promptly notify Pfizer, Janssen Research & Development, the IRB and FDA if the study is terminated for any reason.

### **15.7 Ethics and GCP**

This study will be carried out in compliance with the protocol and Good Clinical Practice, as described in:

- ICH Harmonized Tripartite Guidelines for Good Clinical Practice 1996
- US 21 Code of Federal Regulations dealing with clinical studies (including parts 50 and 56 concerning informed consent and IRB regulations)
- Declaration of Helsinki, concerning medical research in humans (Recommendations Guiding Physicians in Biomedical Research Involving Human Subjects, Helsinki 1964, amended Tokyo 1975, Venice 1983, Hong Kong 1989, Somerset West 1996)

The investigator agrees to adhere to the instructions and procedures described in it and thereby to adhere to the principles of Good Clinical Practice to which it conforms.

### **15.8 Compliance with Trial Registration and Results Posting Requirements**

Under the terms of the Food and Drug Administration Modernization Act (FDAMA) and the Food and Drug Administration Amendments Act (FDAAA), the sponsor-investigator of the trial is solely responsible for determining whether the trial and its results are subject to the requirements for submission to the Clinical Trials Data Bank, <http://www.clinicaltrials.gov>. Information posted will allow subjects to identify potentially appropriate trials for their disease conditions and pursue participation by calling a central contact number for further information on appropriate trial locations and study site contact information.

## **16. MULTI-CENTER GUIDELINES**

### **16.1 Study Documentation**

Each participating site is responsible for submitting copies of all relevant regulatory documentation to the Coordinating Center. The required documents include, but are not limited to the following: local IRB approvals (i.e., protocol, consent form, amendments, patient brochures and recruitment material, etc.), each participant's informed consent, enrollment form, eligibility checklist and tissue block registration, summary of unanticipated problems or protocol deviations, and documentation of expertise of the investigators. The Coordinating Center will provide each participating site with a comprehensive list of the necessary documents. It is the responsibility of the participating sites to maintain copies of all documentation submitted to the Coordinating Center.

The requirements for data management, submissions, and monitoring are outlined below. The TBCRC participating sites will submit all the research related information (source documents and research records – IRB approval documents, patient registration list, CRF info, toxicity assessments, tumor measurements/ responses, etc.) within 2 weeks of the patient's visit to the Coordinating Center Data Manager, who will upload it on Oncore at the appropriate time points: prior to study initiation, when patients are enrolled, and monthly throughout the study. The Coordinating Center Data Manager will have data entered into Oncore within 1 week of receiving the information. Personnel from the VICC Clinical Trial Shared Resource will monitor the trial and may periodically visit the investigative site to assure proper conduct of the trial and proper

collection of the data. The investigators at other sites will allow the monitor to review all source documents used in the preparation of the case reports.

## 16.2 Records Retention

U.S. FDA regulations (21 CFR §312.62[c]) require that records and documents pertaining to the conduct of this study and the distribution of investigational drug, including CRFs, consent forms, laboratory test results, and medication inventory records, must be retained by each Principal Investigator for 2 years after marketing application approval. If no application is filed, these records must be kept 2 years after the study is discontinued and the U.S. FDA and the applicable national and local health authorities are notified.

Following closure of the study, each participating center will maintain a copy of all site study records in a safe and secure location. The Coordinating Center will inform the investigator at each site at such time that the records may be destroyed.

## 16.3 Publication

It is understood that any manuscript or releases resulting from the collaborative research will be circulated to all participating sites prior to submission for publication or presentation.

Any formal presentation or publication of data from this trial may be published after review and comment by Janssen Research & Development and prior to any outside submission. Janssen Research & Development will receive copies of any intended communication in advance of publication (at least twenty-one working days for presentational materials and abstracts and thirty working days for manuscripts). Principal Investigator/Institution shall have the final authority to determine the scope and content of its publications, provided such authority shall be exercised with reasonable regard for the interests of Janssen Research & Development and, in accord with the trial contract shall not permit disclosure of Pfizer, Inc. and Janssen Research & Development confidential or proprietary information. Additionally, any publication of study data and results must conform to the publications policy as stated the Translational Breast Cancer Research Consortium's (TBCRC) "Policies and Procedures".

# 17. STATISTICAL CONSIDERATIONS

## 17.1 Study Design/ Endpoints

This is an open-label phase Ib multi-institution trial that evaluates the safety profile/tolerability (DLT, MTD and RP2D determination) and anti-tumor effect (PFS, CBR and ORR determination) of the combination of palbociclib, fulvestrant and erdafitinib in post-menopausal patients with ER+/HER2-/FGFR-amplified metastatic breast cancer. Since a phase II study is currently being planned, tolerability and experience with this combination over a period of time of at least 8-16 weeks is desirable. Hence, in addition to an MTD, we are proposing a "highest tolerable dose", to minimize the risk for unexpected DLT and ensure good tolerability of study drugs in future phase II trials.

## 17.2 Sample Size and Statistical Analysis

### 17.2.1 Primary endpoint

Demographic and baseline patient characteristics will be summarized. Adverse events will be classified by type, incidence, severity, and causality. All adverse events will be summarized by patient, dose level, and disease. All patients who received at least 4 weeks of study treatment drugs (unless DLTs observed) will be included in the **safety** portion of the trial, and all patients who received at least 8 weeks of erdafitinib will be included in the **tolerability** portion of the trial.

In the phase Ib escalation component of the trial, the MTD will be defined using the recently developed adaptive design known as the modified toxicity probability interval (mTPI) method. The mTPI design uses a Bayesian framework with a beta/binomial hierarchical model to compute the posterior probabilities of three intervals that reflect the relative distance between the toxicity rate of each dose level to the target toxicity probability. That is, the mTPI design replaces the 3 + 3 rules with a model-based inference on the toxicity probability intervals and has been shown to be safer and more reliable than the 3+3 design. The first cohort of patients (3 patients) in each arm will be started at dose level 1, and each patient will be observed for 4 weeks on the specified dose. The maximum tolerated dose (MTD) will be defined as the highest dose at which 20% of the patients experienced a DLT. The levels of uncertainty around the true target toxicity  $p_T$  are (0.05, 0.05), which define the proper dosing interval as  $(p_T - 0.05, p_T + 0.05)$ . Each cohort has 3 patients. In **Table 17.2.1**, the columns are the numbers of patients treated so far at the current dose level, and the rows are the corresponding numbers of patients experiencing toxicity. The entries of the table are dose-finding decisions—E, S, and D—representing escalating the dose, staying at the same dose, and de-escalating the dose, respectively. In addition, decision U means that the current dose level is unacceptable because of high toxicity and should be excluded from the trial. For example, when one of three patients experiences toxicity, the decision is to stay at the current dose level. This means that the next cohort of 3 patients will be treated at the same dose level currently being used. If zero of three patients experiences toxicity, the decision is to escalate. This means that the next cohort of 3 patients will be treated at the next-higher dose level. If three of three patients experiences toxicity, the decision is DU—to de-escalate to the next-lower dose level and exclude the current dose from the trial which is considered unacceptably toxic.

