	
Common Terminology Criteria for Adverse Events, Version 4.03, grade 3]
 

○ QTcF <math>\geq</math> 480 msec on screening EKG

○ Known history of QT/QTc prolongation or Torsades de Pointes (TdP)

○ ST depression or elevation of <math>\geq</math> 1.5 mm in 2 or more leads

○ Diarrhea of any cause <math>\geq</math> CTCAE grade 2 that does not resolve within a few days under adequate treatment

○ Psychiatric illness/social situations that would compromise patient safety or limit compliance with study requirements including maintenance of a compliance/pill diary

○ Symptomatic brain metastases (patients with a history of brain metastases must be clinically stable for more than 4 weeks from completion of radiation treatment and off steroids)

○ Known history of chronic liver or renal failure

○ Poor wound healing capacity

Study Assessments	
Safety Assessment:
 

● History, physical exam, and routine blood work such as blood counts and comprehensive metabolic panel will be performed on day 1 of each treatment cycle.

● Analyses will be performed for all patients having received at least one dose of study drugs. The study will use the NCI CTCAE v4.03.

 
Anti-tumor Assessments:
 

● CT scans of the chest, abdomen, and pelvis and bone scan (when applicable) are to be performed approximately every 8 weeks

 
Exploratory Assessments:
 

● Tumor tissue collection: baseline

● Plasma collection: every other month. cfDNA will be performed at baseline, at 4 weeks after treatment initiation (Cycle 2 Day 1), and at disease progression (end-of-treatment)

● Pharmacodynamic studies: Day 1 and 15 of cycles 1 and 2 (for escalation portion only)

● Pharmacokinetic studies: Day 1 and 15 of cycles 1 and 2 (for escalation portion only)

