### 7.4 Definition of Dose-Limiting Toxicity (DLT)

Any of the following events that occur during cycle 1 (first 4 weeks) will be considered a DLT when classified as possibly, probably or definitively related to investigational study treatment (according to NCI CTEP Adverse Event Reporting Requirements). Apart from the criteria listed below, if a lower grade AE leads to a dose interruption of more than 21 consecutive days of erdafitinib for the first 4 weeks of Cycle 1, this AE will be considered a DLT; patients must receive at least 75% of study drug during cycle 1 in order to be evaluable for the DLT observation period. Whenever a patient experiences toxicity that fulfills the criteria for a DLT, treatment with the study drug responsible for the toxicity will be interrupted (patient may continue the remainder study drugs) and the toxicity will be followed up. The Protocol Chair must be notified immediately of any DLT:

TOXICITY	DLT CRITERIA
Blood and lymphatic system disorders	Anemia CTCAE Grade $\geq$ 3 will not be considered DLT unless judged to be a hemolytic process secondary to erdafitinib.
	Febrile neutropenia CTCAE Grade $\geq$ 3
	ANC CTCAE Grade 3 for > 14 consecutive days
	ANC CTCAE Grade 4
	Platelet count CTCAE Grade 3 for > 7 consecutive days and/or with signs of bleeding
	Platelet count CTCAE Grade 4
Ocular disorders	CTCAE Grade $\geq$ 2 for > 21 days CTCAE Grade $\geq$ 3
General disorders and administration site conditions	Fatigue CTCAE Grade 3 for > 7 consecutive days
Skin and subcutaneous tissue disorders	Skin, mucosal or nail toxicity CTCAE Grade $\geq$ 3 for > 72 hours
Hyperphosphatemia	Phosphorus level $\geq$ 7.0 mg/dL for > 14 days despite treatment
GI disorders a	Diarrhea CTCAE Grade $\geq$ 3 for $\geq$ 48 hrs, despite the use of anti-diarrhea therapy
	Nausea/vomiting CTCAE Grade $\geq$ 3 for $\geq$ 48 hrs, despite the use of anti-emetic therapy
	Constipation CTCAE Grade $\geq$ 3 for $\geq$ 48 hrs, despite the use of anti-constipation therapy
Investigations b	Blood bilirubin c CTCAE Grade 2 for > 7 consecutive days or $\geq$ Grade 3
	AST or ALT CTCAE $\geq$ Grade 3
	Alkaline phosphatase CTCAE $\geq$ Grade 3
Other hematologic and non-hematologic toxicities	Any other CTCAE $\geq$ Grade 3 toxicity for > 7 consecutive days (except decreased lymphocyte count [lymphopenia] that is not clinically significant)

TOXICITY	DLT CRITERIA

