## 7.9 Criteria for Removal from Study

Participants will be removed from study when any of the criteria listed in Section 7.10 applies. All patients who initiate protocol treatment will be included in the safety analysis, and all patients who initiate protocol treatment and receive at least 8 weeks of treatment will be included in overall evaluation of response. All reasons for discontinuation of therapy should be documented clearly in the medical record.

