## 7.10 Discontinuation of Treatment

The reasons for discontinuation or protocol treatment include:

- Evidence of disease progression during treatment at the discretion of the treating investigator
- Non-compliance with the study protocol, including, but not limited to not attending the majority of scheduled visits. The Protocol Chair will determine when non-compliance should lead to removal from study. Note: These patients will still be included in the overall evaluation of safety and response
- Unacceptable major toxicity. Note: These patients will still be included in the overall evaluation of safety and response

- Intercurrent illness or condition that would, in the judgment of the treating investigator, affect assessment of clinical status to a significant degree or require discontinuation of study treatment
- At subject's own request. Note: The reason for discontinuation from the study must be documented. These patients will be included in the overall evaluation of safety and response if any protocol therapy was administered prior to withdrawal
- Study is closed for any reason (e.g. new information shows that the patient's welfare would be at risk if she continued study treatment)
- General or specific changes in the participant's condition render the participant unacceptable for further treatment in the opinion of the treating investigator
- Patients that require a dose delay of > 28 days. If the delay is due to a cause unrelated to study participation, the patient will have the opportunity to continue study if beyond the first 8 weeks of treatment, if clinical benefit is seen, and if deemed eligible to do so by the Protocol Chair of the study
- If the patient requires dose reduction below dose level -1, the patient should be discontinued from the study unless deemed to have clinical benefit that would outweigh the risk. A discussion with the Protocol Chair should be carried out prior to final decision on discontinuation

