### 12.1 Definitions

Evaluable for toxicity: All patients will be evaluable for toxicity from the time of their first administration of study treatment drugs.

Evaluable for objective response: Only those patients who have measurable disease present at baseline, have received at least one cycle of therapy, and have had their disease re-evaluated will be considered evaluable for response. These patients will have their response classified according to the definitions stated below.

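### Section 17.2.1 limits the safety set to patients with 4 weeks of study drugs or a DLT, while other sections count everyone treated; if it governs the adverse event tables, non-DLT toxicity is understated

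*Combined protocol and SAP*

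**What the plan says.** All references are to the combined protocol and SAP. Section 17.2.1 opens its account of the primary endpoint with the adverse event summaries: "All adverse events will be summarized by patient, dose level, and disease". It gives no denominator there. It then defines membership of the safety portion with the words "All patients who received at least 4 weeks of study treatment drugs (unless DLTs observed) will be included in the", and sets a separate 8-week erdafitinib condition for the tolerability portion.

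Other places are wider:

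- Synopsis, Safety Assessment: "Analyses will be performed for all patients having received at least one dose of study drugs".
- Section 7.9: "All patients who initiate protocol treatment will be included in the safety analysis".
- Section 12.1: "All patients will be evaluable for toxicity from the time of their first administration of study treatment drugs".
- Section 7.10 keeps particular groups who stop early. For toxicity it reads "Unacceptable major toxicity. Note: These patients will still be included in the overall evaluation of safety and response". For patients who stop at their own request it reads "These patients will be included in the overall evaluation of safety and response if any protocol therapy was administered prior to withdrawal". Patients removed for non-compliance are kept as well.
- Section 17.3, in the statistical chapter itself, requires a safety assessment of all included patients, even those who were ineligible or had major treatment deviations.

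DLT evaluability is defined elsewhere. Section 7.4 asks for at least 75% of study drug in cycle 1, and section 7.11 uses the same 75% in its rule for calling a patient not evaluable and replaceable.

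**The concern.** Safety and tolerability is the primary objective, and 17.2.1 is where an analyst would look first for the population. The only set that section labels safety depends on completing 4 weeks of drug. Tables built on it would describe mainly patients who coped with the first cycle, plus those with a formal DLT. Patients who gave up early because of toxicity short of a DLT would be missing from both numerator and denominator. In a trial of 26 to 35 patients, losing two or three of them visibly changes a percentage, and those percentages describe the combination that is meant to go on to phase II.

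**Working it through.** No figure in the plan depends on the safety set, so there is none to reproduce. The check compares the rules patient by patient, then works out how far the choice can move a rate.

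**Step 1: who is counted under each rule**

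| Patient | Any-treatment rule (synopsis, 7.9, 12.1) | Section 17.2.1 |
|---|---|---|
| DLT in cycle 1, then stops | in | in |
| Stops all study drugs in week 3 for related Grade 2 toxicity not ruled a DLT | in | out |
| Stops all study drugs before week 4 for an event judged unrelated | in | out |
| Stops all study drugs after day 21, no DLT | in | out |
| Stops one oral drug before week 4, continues the others | in | unclear: 17.2.1 does not say whether 4 weeks of all drugs or of any drug is needed |

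The fourth row also separates 17.2.1 from the DLT-evaluable rule. For daily erdafitinib, 75% of 28 days is 21 days. That patient can be DLT-evaluable under 7.4 and still fall outside the safety portion.

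**Step 2: how much the DLT exception rescues**

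Under 7.4 a DLT must be at least possibly related, occur in cycle 1 and meet a listed threshold. A lower-grade event counts if it interrupts erdafitinib for more than 21 consecutive days in cycle 1, and may count, after discussion with the Protocol Chair, if the interruption exceeds 14 consecutive days. If the first missed dose is on day 15, days 15 to 28 give 14 missed days. Within cycle 1 that exceeds neither limit. An unrelated event can never qualify.

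**Step 3: size for non-DLT events**

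Let N be the number treated, k the early stoppers dropped (all with the event), and y the number with the event among the other N − k.

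- Any-treatment rate: (y + k)/N
- 4-week rate: y/(N − k)
- Difference: (k/N) × [1 − y/(N − k)], so never more than k/N

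N of 26 and 35 are the protocol's limits and 30 lies between them. Every k and y is an assumption.

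| N | k | y | Any-treatment | 4-week | Difference (points) |
|---|---|---|---|---|---|
| 30 (early stops for toxicity) | 3 | 0 | 3/30 = 10.0% | 0/27 = 0% | 10.0 |
| 30 | 3 | 12 | 15/30 = 50.0% | 12/27 = 44.4% | 5.6 |
| 30 | 3 | 17 | 20/30 = 66.7% | 17/27 = 63.0% | 3.7 |
| 26 | 2 | 5 | 7/26 = 26.9% | 5/24 = 20.8% | 6.1 |
| 35 | 2 | 7 | 9/35 = 25.7% | 7/33 = 21.2% | 4.5 |

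The third row uses y close to the 62.0% Grade 3 or 4 neutropenia that section 3.2.1 quotes for palbociclib with fulvestrant. With k from 1 to 4 and about 20% affected among the rest, the difference runs from 2.3 points (N = 35, k = 1: 8/35 = 22.9% against 7/34 = 20.6%) to 12.6 points (N = 26, k = 4: 8/26 = 30.8% against 4/22 = 18.2%).

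**Step 4: direction for DLTs**

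With d DLTs, all retained, the rate is d/N among all treated and d/(N − k) under 17.2.1. For N = 30 and k = 3 the second is 30/27 = 1.11 times the first. The DLT rate goes up.

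**The case against.** The strongest reply is that the sentence is a mislabelled DLT set. It stands under the primary endpoint heading, the primary endpoints are DLT in the first 4 weeks and the MTD, the threshold is 4 weeks, DLT patients are exempt, and the text moves straight on to the mTPI design. The sentence about summarizing adverse events carries no exposure limit, and 17.3 points to including everyone. This may well be the intention. But the text says safety, does not match the 75% rule in 7.4, and would need correcting on that reading too. What stands is that the loss is conditional: it occurs only if the 4-week rule is used as the adverse event denominator.

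A reader might infer more than the documents support, in four ways:

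- *That single-drug stops are lost.* Section 7.4 says of Grade 3 or higher anemia that it "will not be considered DLT unless judged to be a hemolytic process secondary to erdafitinib", and section 8.4 stops palbociclib at Grade 4. Likewise 8.4 stops erdafitinib for Grade 4 constipation, which is not a DLT if it lasts under 48 hours. But section 8.5 allows the remaining drugs to continue, so these patients may still reach 4 weeks of study treatment.
- *That every low-grade early stop is lost.* The discretionary 14-day rule in 7.4 sets no explicit cycle 1 limit on the length of the interruption, so a permanent stop in week 3 for a related event could be ruled a DLT and kept.
- *That early deaths disappear.* Section 13.3.1 makes any death within 30 days of the last dose a serious adverse event, and 17.3 gives early deaths their own categories.
- *That the primary DLT and MTD result is biased downward.* Every DLT is retained, and the phase II dose rule uses the separate 8-week tolerability criterion of 15 out of 20.

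**Conclusion.** The conflict is real and unresolved. Section 17.2.1 is narrower than the any-treatment rule in the synopsis, 7.9 and 12.1, it can drop stoppers whom 7.10 keeps, it disagrees with 17.3, and no section takes precedence. Section 7.10 covers named groups only, so it supports the wider rule without defining it.

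If 17.2.1 sets the denominator, those clearly lost are patients who stop all study drugs before week 4 with toxicity not counted as a DLT or with an event judged unrelated. Non-DLT adverse event rates and early-discontinuation rates are then too low. On assumed counts the effect is about 2 to 13 percentage points for 26 to 35 treated patients with 1 to 4 such stoppers, and it is nil if there are none. The 10% against 0% comparison shows the mechanism; the zero follows from the definition. The documents do not support a claim that the DLT rate or the MTD decision is made to look safer.

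**What to change.** In 17.2.1, define the safety set for all adverse event summaries as every patient who received one dose or more of any study drug, in line with the synopsis, 7.9 and 12.1.

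If the 4-week sentence was meant for DLT evaluation, take the word safety out of it and refer instead to a single DLT-evaluable definition, used only for the mTPI decisions. Simply relabelling the 4-week rule would not do, because it would contradict the 75% condition in 7.4 and the replacement rule in 7.11. Those passages have to be reconciled first.

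The cost is one sentence for the safety set and a short cross-section edit for the DLT-evaluable set. Adverse events are already collected from consent until 30 days after the last dose (section 13.1), so no new data and no change in sample size are needed. The downside is that reported toxicity rates may look slightly less favourable.
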